8.3.5.1. Virus Serology

Testing for HIV-1 and HIV-2 is required for all participants prior to enrollment. Participants who are HIV antibody positive will not be enrolled.

Similarly, participants who are positive at the Screening Visit for HBsAg, anti-HBc with negative anti-HBs, or HCV antibody positive (except for participants with documented successful treatment and documented sustained viral response) will not be enrolled.

8.3.6. Pregnancy

Pregnancy testing must be performed on all women of childbearing potential (WOCBPs) at protocol-specified time points in the SoA (Section 1.3). Pregnancy tests (urine or serum) may also be performed at any time during the study at the Investigator's discretion.

A negative pregnancy test is required for WOCBPs before study drug administration.

- Any female participant who becomes pregnant while participating in the study will be discontinued from the study drug.
- If a pregnancy is reported, the Investigator must immediately inform Alexion within 24 hours of awareness of the pregnancy and follow the procedures outlined in Section 10.6.3.
- Details of all pregnancies in female participants and female spouses/partners of male participants will be recorded and the pregnancy followed to term and Alexion notified regarding the outcome, even if the participant discontinues the study drug or withdraws from the study. The corresponding infant must be followed-up with for 3 months postpartum.
- Pregnancy is not considered as an AE unless there is a suspicion that the study drug may have interfered with the effectiveness of a contraceptive medication. However, complications of pregnancy and abnormal outcomes of pregnancy are AEs and may meet the criteria for an SAE (eg, ectopic pregnancy, spontaneous abortion, intrauterine fetal demise, neonatal death, or congenital anomaly) (Section 10.3.2). Elective abortions without complications should not be reported as AEs.

8.4. Adverse Events and Serious Adverse Events

The definitions of AEs and SAEs can be found in Section 10.3.

All AEs will be reported to the Investigator or qualified designee by the participant (or, when appropriate, by a caregiver, surrogate, or the participant's legally authorized representative).

The Investigator and any qualified designees are responsible for detecting, documenting, and recording events that meet the definition of an AE or SAE and remain responsible for following up AEs that are serious, considered related to the study drug or study procedures, or that caused the participant to discontinue the study drug (see Section 7).

Procedures for recording, evaluating, follow-up, and reporting AEs and SAEs are outlined in Section 10.3.

8.4.1. Time Period and Frequency for Collecting AE and SAE Information

All AEs (serious and nonserious) will be collected from the signing of the ICF until Week 86 or, if the participant discontinues study drug early, 8 weeks (56 days) after last dose of study drug is administered.

All SAEs will be recorded and reported to Alexion or the designee immediately and under no circumstance should this exceed 24 hours, as indicated in Section 10.3. The Investigator will submit any updated SAE data to Alexion within 24 hours of it being available.

Investigators are not obligated to actively seek AE or SAE data after conclusion of the study participation. However, if the Investigator learns of any SAE, including a death, at any time after a participant has been discharged from the study, and he/she considers the event to be reasonably related to the study drug or study participation, the Investigator must promptly notify Alexion.

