Table 3: Schedule of Activities During the Extension Period: Week 26 Dose Administration, Week 34 to Week 50 Visits (LN Cohort)

Period	Extension Period				Eval. for Renal Flare and Extrarenal SLE Flare and Suboptimal Response	Notes Additional visits can be performed as needed. An ED Visit should be performed if participants discontinue early.
Visit	11	12	13	14		
Week	W26	W34	W42	W50/ED ^a		
Days and Window	D183	D239 ± 7	D295 ± 7	D351 ± 7		
Adverse events	Continuous monitoring				X	
Clinical chemistry		X	X	X	X	
Hematology and coagulation		X	X	X		
Urinalysis and sediment		X	X	X		Obtain sample from a morning void prior to dosing
Participant safety card review		X	X	X	X	Confirm participants carry safety card at all times
Pharmacokinetic and Pharmacodynamic Assessments						
Blood samples for PK/PD		T/P	T/P	X		Collect samples at any time during the Week 50/ED Visit
Blood samples for ADA		T	T	X		Collect samples at any time during the Week 50/ED Visit
Exploratory Assessments						
SF-36				X		
EQ-5D-5L				X		
FACIT-Fatigue				X		
SLEDAI-2K				X	X	Perform as needed for evaluation of Extrarenal SLE Flare
Blood samples for anti-dsDNA and anti-C1q				X	X	
Blood and urine samples for biomarkers		X	X	X	X	
Optional kidney biopsy ^f				X ^g	X ^f	Send the local pathology report and microscopy slides to the Central Pathology Laboratory (Section 8.1.5.3)
Administration of Study Intervention						
Allowed concomitant LN therapy	Continuous monitoring				X	Section 6.5.1
Ravulizumab or placebo	X	X	X			Administer after all other required tests/procedures

Table 3: Schedule of Activities During the Extension Period: Week 26 Dose Administration, Week 34 to Week 50 Visits (LN Cohort)

Note: During the Extension Period, participants in the LN cohort will continue to receive their randomized allocation of study drug (ravulizumab or placebo).

^a For participants who discontinue the study prior to the end of the Extension Period, the ED Visit should be completed as soon as possible. In addition, a Follow-up Phone Call will be performed 8 weeks following the participant's last dose of study drug to collect concomitant medications, nonpharmacological therapies and procedures, and AEs.

^b Weight should be obtained at every visit and measured predose on dosing visits. The dose regimen is based on the last recorded study visit body weight. If the study drug is prepared the night before a visit, the weight from the most recent study visit should be used.

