During the Initial Evaluation Period, all participants will receive a weight-based loading dose of ravulizumab or placebo on Day 1, followed by weight-based maintenance doses of ravulizumab or placebo on Day 15 and then q8w thereafter ([Table 8](#)). All participants will receive allowed concomitant therapy consistent with the standard of care for participants with LN and IgAN throughout the study as defined in Section [6.5](#).

During the 24-week Extension Period, participants will continue to receive study drug (ravulizumab or placebo):

- Participants in the LN cohort will continue to receive their randomized allocation of study drug (ravulizumab or placebo) q8w until the end of the Extension Period. Participants will receive additional standard of care therapy in the event of a protocol-defined Renal Flare or Severe Extrarenal SLE Flare. Additional standard of care

therapy for participants with Suboptimal Response is allowed at the clinical discretion of the Investigator in conversation with the Medical Monitor.

- Participants in the IgAN cohort randomized to the placebo group will switch to receive a blinded loading dose of ravulizumab at Week 26 and then open-label weight-based dosing of ravulizumab q8w until the end of the Extension Period.
- Participants in the IgAN cohort randomized to the ravulizumab group will receive a blinded dose of 900 mg ravulizumab at Week 26 and then open-label weight-based dosing of ravulizumab q8w until the end of the Extension Period.

During the 36-week Post-treatment Follow-up Period, participants will continue to receive standard of care, at the discretion of the Investigator, and will be monitored for safety, clinical events of interest, and kidney function.

Participants who discontinue study drug early and agree to remain in the study should continue to attend their scheduled protocol visits until Week 50. During these visits, all assessments except for study drug administration should be performed according to the Schedule of Assessments.

Participants who withdraw from the study will be followed for safety until 8 weeks after the last dose of study drug.

The end of study is defined as the last participant's last visit in the Post-treatment Follow-up Period.

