7. DISCONTINUATION OF STUDY INTERVENTION AND PARTICIPANT DISCONTINUATION/WITHDRAWAL

7.1. Discontinuation of Study Drug

A participant has the right to discontinue study drug at any time.

Participants must permanently discontinue the study drug for any of the following reasons:

- Serious hypersensitivity reaction
- Severe uncontrolled infection
- Serious infusion reaction (such as bronchospasm with wheezing or requiring ventilator support or symptomatic hypotension, refer to Section 10.4) or serum sickness-like reactions manifesting 1 to 14 days after drug administration
- Use of disallowed medication as defined in Section 6.7.2
- Pregnancy or planned pregnancy
- Participant is unblinded during the Initial Evaluation Period

In addition, the study drug may be permanently discontinued for any of the following reasons:

- Adverse event that would, in the opinion of the Investigator, make continued participation in the study an unacceptable risk
- Deviation(s) from the protocol
- Significant non-compliance
- Alexion or the Investigator deems it is necessary for the participant
- Study termination

The reason for discontinuation of study drug will be recorded in the source documents and CRF.

If the study drug is definitively discontinued, every effort should be made to have the participant continue the study visits as per the SoA through Week 50/EoS. If a participant discontinues study drug due to an AE, including SAEs, the event should be followed as described in Section 10.3.3.

Participants who discontinue study drug and remain on study may receive treatment consistent with local standard practice for their disease per Investigator judgment, as applicable.

If the participant does not agree to continue with the study visits, the following activities should be completed:

- Early Discontinuation Visit should be performed as outlined in the SoA (Section 1.3).
- A Follow-up Phone Call will be performed 8 weeks following the participant's last dose of study drug to collect information on concomitant medications, nonpharmacological therapies and procedures, and AEs.

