8.3. Safety Assessments

8.3.1. Participant Safety Card

Before the first dose of the study drug, a Participant Safety Card will be provided to participants to carry with them at all times until 8 months after the final dose of study drug. The card is provided to increase participant awareness of the risk of meningococcal infection and promote quick recognition and disclosure of any potential signs or symptoms of meningococcal infection experienced during the course of the study and to inform participants on what actions must be taken if they are experiencing signs or symptoms of infection.

At each visit throughout the study, the study staff will ensure that the participant has the Participant Safety Card.

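### Protocol 8.4.1 ends AE collection 56 days after the last dose for everyone who stops study drug early, including participants whom Sections 1.1, 4.1 and 7.1 and Tables 1 to 4 keep under assessment to Week 50

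*Protocol*

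**What the plan says.** Protocol 8.4.1 has two end dates. The general rule is "All AEs (serious and nonserious) will be collected from the signing of the ICF until Week 86 or"; the alternative to Week 86 is, "if the participant discontinues study drug early, 8 weeks (56 days) after last dose of study drug is administered". It does not separate a participant who stops drug and stays from one who withdraws.

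Protocol 4.1 (repeated in 1.1 and in SAP 1.2) addresses the first of these groups: "Participants who discontinue study drug early and agree to remain in the study should continue to attend their scheduled protocol visits until Week 50". It adds: "During these visits, all assessments except for study drug administration should be performed according to the Schedule of Assessments". Section 7.1 says that "every effort should be made to have the participant continue the study visits as per the SoA through Week 50/EoS". In Tables 1 to 4 the adverse-event row reads "Continuous monitoring", with no exemption for participants off drug.

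The 8-week limit for early stoppers appears in two other places, each time for people who are leaving. Section 4.1 gives it to participants who withdraw from the study. Section 7.1 asks for the 8-week phone call when the participant will not continue with visits.

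Section 8.13 gives a third rule. It ends safety follow-up 8 weeks after the last dose for all participants, with the final safety evaluation at Week 50 (LN) or by phone at Week 52 (IgAN). Table 5 nevertheless schedules an AE phone contact at Week 86, as 8.4.1 implies.

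**The concern.** A site with a participant who has stopped drug but still attends cannot follow both instructions. At a visit more than 56 days after the last dose, 8.4.1 says AE and SAE collection is over, while 4.1 and the schedule say AEs are assessed.

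These participants are not a random subset. Section 7.1 makes stopping mandatory for, among other reasons, severe uncontrolled infection, serious hypersensitivity and serious infusion reaction. If sites follow 8.4.1, new events in this group after 56 days go uncollected, while participants who complete dosing are collected to Week 86. If some sites follow 8.4.1 and others the schedule, ascertainment also varies by site. Safety outputs that extend beyond 56 days would then depend on treatment status rather than on study participation.

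**Working it through.** **Inputs**
- Collection limit after an early stop: 8 weeks (8.4.1). 8 × 7 = 56 days, which matches the protocol's own conversion.
- Week 50 = Day 351 (Tables 3 and 4). Week 86 = Day 603 (Table 5). Nominal days are used and visit windows ignored.
- Dosing days: 1, 15, 71, 127 and 183 in both cohorts, then 239 and 295 (LN) or 197, 253 and 309 (IgAN) (Sections 4.1 and 6.1, Tables 3, 4 and 9).

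**Formula**

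End of collection = last-dose day + 56. Gap = 351 − (last-dose day + 56), not below zero.

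| Last dose | Cohort | Collection ends | Gap to Week 50 |
|---|---|---|---|
| Day 1 | both | Day 57 | 294 days (42 weeks) |
| Day 15 | both | Day 71 | 280 days (40 weeks) |
| Day 71 | both | Day 127 | 224 days (32 weeks) |
| Day 127 | both | Day 183 | 168 days (24 weeks) |
| Day 183 | both | Day 239 | 112 days (16 weeks) |
| Day 197 | IgAN | Day 253 | 98 days (14 weeks) |
| Day 239 | LN | Day 295 | 56 days (8 weeks) |
| Day 253 | IgAN | Day 309 | 42 days (6 weeks) |
| Day 295 | LN | Day 351 | 0 |
| Day 309 | IgAN | Day 365 | 0 |

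The gap is zero only when the last dose is the final scheduled one. If at least one scheduled dose is missed at the end, it is at least 56 days (LN) or 42 days (IgAN). For an LN participant last dosed on Day 15, Tables 1 and 3 still schedule seven visits after Day 71 (Days 99, 127, 155, 183, 239, 295 and 351).

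**Comparison with completers, taking 8.4.1 and Table 5 at face value**

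LN: 603 − 295 = 308 days after the last dose. IgAN: 603 − 309 = 294 days. Early stoppers have 56 days.

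**Which outputs this reaches**
- TEAE and TESAE tables: not reached. Protocol 9.4.2.1 and SAP 5.6.2 and 6.1.7 end treatment emergence at about 56 days after the last dose for all participants.
- Post-treatment AEs: SAP 5.6.2 puts these in by-participant listings, so the listings are reached.
- Participants who died on study: counted under SAP 5.6.2.1 with no 56-day limit stated.
- Meningococcal AEs, the only AESI (Protocol 8.4.6): SAP 5.6.2.5 promises a table and a listing, and SAP 6.1.8 defines the search. Neither states a treatment-emergent limit.

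**The case against.** The strongest reply is that 8.4.1 is loose wording for early withdrawal. Read with 4.1 and 7.1, the 56 days is meant for people who leave, and a site following the schedule would keep asking about AEs. That is probably the intent. But 8.4.1 is the section that defines the collection period, and its trigger as written is stopping drug. A site relying on it would not be in breach.

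Existing safeguards also narrow the loss. An AE that led to stopping must be followed (7.1, 8.4), and SAEs are followed to resolution or stabilization (8.4.3), so only new-onset events are at issue. Section 8.4.1 also obliges the investigator to report an SAE learned of after discharge and judged reasonably related. That duty is mandatory but passive. It depends on a causality judgement, omits nonserious AEs, and is framed for people already discharged, not for those still attending. Deaths are the least likely to be missed, since SAP 5.2 also tabulates reasons for leaving the study.

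A reader might infer that the main AE and SAE incidence comparison is made over unequal observation because of 8.4.1. The documents do not support this. Those tables stop at about 56 days for everyone, and any difference in time at risk within them comes from exposure, which changing 8.4.1 would not alter.

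A reader might also infer that the cut-off falls inside a stated 8-month risk period. The protocol names no such period. Participants are given the safety card "to carry with them at all times until 8 months after the final dose of study drug" (8.3.1), and contraception and breastfeeding advice use the same 8 months. The card concerns meningococcal risk, so the inference is understandable, but it remains an inference.

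**Conclusion.** The contradiction stands. For participants who stop drug and agree to remain, 8.4.1 is inconsistent with 1.1, 4.1, 7.1 and Tables 1 to 4, and no other passage resolves it. Followed literally, it leaves 0 to 294 days of attended study time without collection of new-onset AEs, depending on the last-dose day. For participants who withdraw from the study, the 8-week limit agrees with 4.1.

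The consequence is limited to outputs beyond 56 days: post-treatment AE and SAE listings, on-study deaths and the meningococcal summary. For the meningococcal table, this assumes that the general exclusion of post-treatment AEs from summary tables in SAP 5.6.2 does not apply. If it does, only the listing is affected.

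The size by arm cannot be computed, because the documents give no discontinuation rates by arm. The only related figure is the 10% dropout anticipated in Protocol 9.2 (0.10 × 60 = 6 per cohort), and that does not show how many would stop drug and stay.

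The comparison with completers also depends on 8.4.1 and Table 5 prevailing over 8.13. If 8.13 governs, safety follow-up ends at 8 weeks for everyone, but the conflict with scheduled AE monitoring to Week 50 remains for early stoppers.

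**What to change.** Amend Protocol 8.4.1 so that the end of AE and SAE collection follows study participation:
- Participants who stop drug but remain in the study have AEs and SAEs collected at least through their last attended visit (Week 50 if they stay that long).
- The 56-day limit applies only to participants who withdraw from the study.

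In the same edit, reconcile 8.13 (8 weeks for all) with 8.4.1 and Table 5 (Week 86). State whether retained early stoppers also have the Week 86 phone contact. Sections 1.1 and 4.1 ask them to attend only to Week 50, while 7.1 writes Week 50/EoS and Table 5 places EoS at Week 86.

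The cost is a short text change and a small amount of extra data entry, since AE monitoring to Week 50 is already scheduled. Extending collection to Week 86 would add one phone contact per retained participant. The 56-day treatment-emergent definition need not change.

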8.4.2. Method of Detecting AEs and SAEs

The method of recording, evaluating, and assessing causality of AE and SAE and the procedures for completing and transmitting SAE reports are provided in Section 10.3.

Care will be taken not to introduce bias when detecting AEs and/or SAEs. Open-ended and non-leading verbal questioning of the participant is the preferred method to inquire about AE occurrences.

8.4.3. Follow-up of AEs and SAEs

After the initial AE/SAE report, the Investigator is required to proactively follow-up on each participant at subsequent visits/contacts. All SAEs will be followed up until resolution, stabilization, the event is otherwise explained, or the participant is lost to follow-up (as defined in Section 7.3). Further information on follow-up procedures is provided in Section 10.3.

8.4.4. Regulatory Reporting Requirements for SAEs

- Prompt notification of an SAE by the Investigator to Alexion is essential so that legal obligations and ethical responsibilities towards the safety of participants and the safety of a study intervention under clinical investigation are met.
- Alexion has a legal responsibility to notify both the local regulatory authority and other regulatory agencies about the safety of a study intervention under clinical investigation. Alexion will comply with country-specific regulatory requirements relating to safety reporting to the regulatory authority, IRBs/ IECs, and Investigators.
- Alexion is required to submit individual suspected unexpected serious adverse reaction (SUSAR) reports (defined in Section 10.3.2) in the format of MedWatch 3500 or CIOMS I Form and forwarded to Investigators as necessary. Consistent with Alexion policy and procedures for blinded clinical studies, these reports to Investigators will be blinded to treatment assignment. In limited circumstances, the blind may be broken in the case of urgent safety issues that could compromise participant safety.
- An Investigator who receives an Investigator safety report describing an SAE or other specific safety information (eg, summary or listing of SAEs) from Alexion will

review and then file it along with the IB and will notify the IRB/IEC, if appropriate according to local requirements.

- Under the EU CTR 536/2014, events other than SAEs (eg, unexpected events) that may impact the benefit-risk balance should be reported. See definitions in Section 10.3.5.

8.4.5. Medication Error, Drug Abuse, and Drug Misuse

Medication error, drug abuse, and drug misuse will be collected from signing of the applicable version of the ICF through the last scheduled procedure shown in the SoA (Section 1.3).

8.4.5.1. Timelines

If an event of medication error, drug abuse, or drug misuse occurs during the study, then the Investigator or other site personnel will report to Alexion or designee immediately but no later than 24 hours of when they become aware of it.

The full definitions and examples of medication error, drug abuse, and drug misuse can be found in Section 10.5.

8.4.5.2. Medication Error

For the purposes of this clinical study a medication error is an unintended failure or mistake in the treatment process for a study intervention that either causes harm to the participant or has the potential to cause harm to the participant.

8.4.5.3. Drug Abuse

Drug abuse is the persistent or sporadic intentional, non-therapeutic excessive use of study intervention for a perceived reward or desired non-therapeutic effect.

8.4.5.4. Drug Misuse

Drug misuse is the intentional and inappropriate use of study intervention for medicinal purposes outside of the authorized product information, or for unauthorized study intervention, outside the intended use as specified in the protocol, including deliberate administration of the product by the wrong route.

8.4.6. Adverse Events of Special Interest

Meningococcal infections will be considered to be adverse events of special interest (AESIs).

8.5. Review of Prior and Concomitant Medications and Procedures

8.5.1. Prior Medications and Procedures

Prior medications and/or vaccines (including vitamins, herbal preparations, and those discussed in the exclusion criteria [Section 5.2]) and procedures (any therapeutic drug, such as surgery/biopsy or physical therapy) that the participant takes or undergoes within 30 days before the start of Screening or during the Screening Period before the first dose of study drug, as well

as any meningococcal vaccine administered within the last 3 years, will be recorded in the participant's CRF.

For participants in the IgAN cohort:

- ACE inhibitors and ARBs during 3 months prior to the first dose
- Blood pressure medications received during the 3 months prior to the first dose

Information regarding the prior use of disease-specific treatment will be recorded for both cohorts, including immunosuppression induction treatment for participants in the LN cohort.

